9.2 Setting

The study population consists of three cohorts of pregnant women (See Section 9.5 for sample size).

Participants will be recruited into the three cohorts concurrently, on the basis of the following inclusion/exclusion criteria:

Cohort 1: Benralizumab-Exposed

Inclusion Criteria:

- Currently pregnant women diagnosed with asthma who contact the OTIS Research Center and who have been exposed to benralizumab for any number of days, at any dose, and at

any time from 8 weeks before the first day of LMP up to and including the end of pregnancy.

- Eligible participants will be currently pregnant women who agree to the conditions and requirements of the study including the interview schedule and release of medical records.

Exclusion Criteria:

- Women who have had exposure to another biologic, used for any indication, anytime during pregnancy or within 8 weeks of LMP.
- Women will not be eligible for Cohort 1 if they first contact the OTIS Research Center after prenatal diagnosis of a major structural birth defect.
- Retrospective cases (outcome of pregnancy known prior to enrollment).
- Women who have enrolled in the current study with a previous pregnancy.

Cohort 2: Treated Diseased Comparison

Inclusion Criteria:

- Currently pregnant women diagnosed with asthma and exposed to asthma medications for any number of days, at any dose, and at any time from LMP up to the date of enrollment, who contact the OTIS Research Center but who were not exposed to benralizumab during pregnancy or within 8 weeks prior to LMP.
- Eligible participants will be currently pregnant women who agree to the conditions and requirements of the study including the interview schedule and release of medical records.

Exclusion Criteria:

- Women with exposure to benralizumab any time during pregnancy or within 8 weeks prior to LMP.
- Women will not be eligible for Cohort 2 if they first come in contact with the OTIS Research Center after prenatal diagnosis of a major structural birth defect.
- Retrospective cases (outcome of pregnancy known prior to enrollment).
- Women who have enrolled in the current study with a previous pregnancy.

Cohort 3: Non-Asthmatic Comparison

Inclusion Criteria:

- Currently pregnant women who contact the OTIS Research Center.
- Eligible women may potentially have been exposed to non-teratogenic agents during this pregnancy.

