9.3.3 Confounders and effect modifiers

The potential confounders/effect modifiers listed below will be considered in multivariable analyses, as well as others that are relevant to each of the study outcomes:

- Maternal and paternal age
- Previous pregnancy history: gravidity and parity, previous spontaneous abortions and elective terminations
- Maternal and paternal race/ethnicity, education, occupation, socioeconomic status
- Pre-pregnancy body mass index
- Previous preterm delivery
- Previous child with birth defect
- Maternal conditions: e.g., depression, diabetes
- Maternal exposures: gestational timing and dose of all over-the-counter and prescription medications, including all asthma medications used during pregnancy; vitamin and

mineral supplements, herbal products; illnesses; fever; vaccinations, travel outside of the U.S.

- Prenatal testing: ultrasound and other prenatal tests; timing in gestation and results
- Pregnancy complications: e.g., pregnancy induced hypertension, gestational diabetes
- Maternal lifestyle habits: cigarette smoking, alcohol consumption and illicit drug use
- Asthma related covariates: Asthma Control Test at each maternal interview, years since diagnosis of asthma, hospitalizations or unscheduled asthma visits for asthma exacerbations throughout pregnancy, use of systemic steroids for asthma exacerbations, and classification of asthma severity at enrollment based on women self-reported prescription classified by ([GINA guidelines, 2016](#)) guidelines.

Methods for identifying and controlling for these confounders and/or effect modifiers are described in Section 9.7.1. The Statistical Analysis Plan (SAP) will provide greater detail on the definitions of, the identification of and the controlling for confounders and/or effect modifiers.

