9.4 Data sources

Maternal Interviews: In all three study groups, data are collected by semi-structured maternal telephone interview on two to four occasions during, and shortly after completion of pregnancy. The interviews include data on exposure timing, dose, and duration for all medications, including benralizumab, taken anytime in pregnancy as well as data on a wide variety of confounders (See Section 9.3.3).

For women exposed to benralizumab or other asthma medications, information on disease severity/symptom control from the Asthma Control Test is obtained directly from the mother at each maternal telephone interview. In addition, information on asthma related hospitalizations and physician visits is collected at the enrollment interview and each of the subsequent maternal interviews. At the conclusion of pregnancy, regardless of the outcome, participants are interviewed about the outcome including presence or absence of birth defects, pregnancy and infant complications and infant size. At this time point the Asthma Control Test questions are asked again to reflect the last four weeks of pregnancy. In addition, asthma treatment regimen at first day of last menstrual period for the current pregnancy according to GINA guidelines will be used to classify disease severity.

Medical Records: Mothers are asked to release medical records to the study investigators from their obstetrician or other obstetric provider, specialty care provider such as allergist/pulmonologist, hospital of delivery, pediatrician, and other health care provider specialists involved in the pregnancy. These records are abstracted and used to validate pregnancy outcomes, collect information on health and growth of the child, and when necessary to provide details regarding timing or dose of benralizumab and other asthma medications in the absence of clear information from maternal report. Self-reported prescriptions used for GINA

classification will be validated with medical record information where available. Pre-defined definitions for each of the study outcomes are used for classification.

Validation of final classification of major birth defects, the primary outcome, that have already been identified by the study Data Coordinator and verified and classified by the Study Manger, is conducted periodically and before each annual and final study report by the study Co-Investigator, a specialist in dysmorphology/teratology.

Table 4 Variables collected per cohort

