9.5 Study size

The proposed sample sizes in each of the three study groups are as follows:

- 200 women exposed to benralizumab at any time 8 weeks prior to LMP and throughout pregnancy
- 300 women with treated asthma, unexposed to benralizumab, aiming to represent the full spectrum of asthma severity with emphasis on severe patients
- 300 non-asthmatic comparison women

The sample size is considered plausible based on the experience of the OTIS research group with previous studies of asthma in pregnancy, but enrollment rates for the current study are unknown. Although it is unknown to what extent benralizumab will be used by pregnant women, experience with recruitment in the omalizumab (Xolair) EXPECT registry provides some support for the proposed sample size. In six years of recruitment, the EXPECT registry recruited 191 exposed pregnancies ([J. Namazy et al., 2015](#)).

No formal statistical hypothesis testing will be done. Point estimates of the rate ratios and associated CI's between the benralizumab exposed cohort and the unexposed cohorts will be used to evaluate the potential risk of benralizumab to mothers and fetuses.

Table 5 is included to contextualize the magnitude of reported relative risks. This outlines the probability of observing rate ratios in excess of different thresholds either by chance (i.e., when the true underlying risk ratio is 1) or when there is a true underlying increase in risk (RR of 1.2, 1.5 or 2), given the planned sample size.

- If the truth is that there is no increase in risk (true RR=1), the current study would have a relatively small probability (<20%) of reporting out an observed relative risk of 1.5 or greater.
- If the truth is that there is a doubling of risk, the current study would have a higher probability of reporting an observed RR greater than 1.5 ($\geq 70\%$), and a smaller probability of reporting out an observed RR < 1.2 ($\leq 13\%$).

Table 5 Probability that observed relative risk point estimates (exposed/unexposed) will exceed different thresholds

Outcome	Prevalence in unexposed cohort	Expected number of Exposed/ Unexposed Asthmatic cohorts		True RR	Probability observed RR exceeds X			
		enrolled	with complete outcome		X=1.2	X=1.5	X=2.0	X=3.0
All major birth defects in live born infants	3%	200/300	180/270	1	0.38	0.19	0.10	0.02
				1.2	0.51	0.29	0.16	0.04
				1.5	0.68	0.45	0.27	0.08
				2	0.87	0.70	0.49	0.18
Preterm birth	7%	200/300	180/270	1	0.30	0.10	0.02	0.00
				1.2	0.50	0.22	0.06	0.00

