9.7.2 Exploratory/sensitivity analyses

Exploratory analyses addressing potential effect modifiers such as Asthma Control Test measures of disease symptom control, and measures of asthma exacerbation will be addressed.

In addition, sub-analyses based on length and gestational timing as well as dose of exposure to benralizumab will be performed.

Stratified analyses based on prenatal diagnostic test performed prior to enrollment in the study will be conducted for the primary endpoint. The purpose of this analysis is to address the inherent bias in excluding women at the time of enrollment in the cohort study who have already received prenatal diagnosis of a major structural birth defects, but including women who have already had a normal result or prenatal diagnosis for major structural birth defects prior to enrollment. Therefore, the planned stratified analysis will compare the birth prevalence of major structural birth defects among the subset of women enrolled in the cohorts prior to prenatal diagnostic testing to detect structural defects (ultrasound for structure, chorionic villus sampling, amniocentesis), to the birth prevalence of major birth defects among the subset of women enrolled in the cohorts after prenatal diagnostic testing to detect structural defects.

Regarding asthma severity, the measures are only captured after enrollment, and in the exposed group only after being on treatment, so they would typically not be included in the analysis as adjustment factors as they could be mediators. However, descriptive analyses of the balance in cohorts on measures of disease severity are presented. Sub-analyses or

sensitivity analyses within disease severity categories can be performed, depending on the distribution of the covariates. This would be described in detail in the SAP.

Sub-analyses excluding chromosomal or known genetic anomalies (classified by study investigators as having a known genetic etiology) will also be conducted. Details will be provided in the SAP.

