9.7.3 General considerations for data analyses

The general approach to controlling for confounding is to evaluate each relevant confounder (from a pre-specified list for each outcome) to determine if inclusion of the confounder in a model containing exposure to benralizumab changes the estimate of the effect of exposure by 10% or more. The confounders will be assessed univariately and those confounders that are identified as meeting criteria described above are incorporated into multivariate analyses as described in the statistical analysis Section 9.7.1, if sample size permits. Further details will be contained in the SAP. Control for confounding by indication is addressed by comparison to the treated disease group. However, as described in exploratory analyses in Section 9.7.2, attention to measures of disease symptom control and underlying severity will also be addressed by subgroup and stratified analysis.

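### Section 9.7.2 leaves asthma severity out of adjustment by default because it is measured too late, but Section 9.4 dates a severity class to LMP and Section 9.3.3 lists severity as a covariate

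*Protocol*

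**What the plan says.** Section 9.7.2 gives two linked reasons for not adjusting for severity. The first is timing: "the measures are only captured after enrollment, and in the exposed group only after being on treatment". The second, possible mediation, comes with the consequence that the section draws from both: "so they would typically not be included in the analysis as adjustment factors as they could be mediators". It adds that balance on severity will be described, and that sub-analyses within severity categories are possible if the covariate distribution allows, with details left to the SAP.

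Three other places bear on this:

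- Section 9.4 says severity will be classified from the "asthma treatment regimen at first day of last menstrual period for the current pregnancy according to GINA guidelines".
- Section 9.3.3 states: "The potential confounders/effect modifiers listed below will be considered in multivariable analyses". Its list includes "classification of asthma severity at enrollment based on women self-reported prescription classified by" the GINA guidelines.
- Section 9.7.3 states: "Control for confounding by indication is addressed by comparison to the treated disease group". Its next sentence says that symptom control and underlying severity will also be handled by subgroup and stratified analysis.

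On the cohorts, Section 7 gives the US indication as severe asthma with an eosinophilic phenotype and puts severe asthma at 5-10% of asthmatic patients. Cohort 2 requires only that women were "exposed to asthma medications for any number of days, at any dose, and at any time from LMP up to the date of enrollment" (Section 9.2). Section 9.5 describes this cohort as "aiming to represent the full spectrum of asthma severity with emphasis on severe patients". Section 9.9 says there is no matching on severity, that the groups may differ, and that recruitment emphasis can be shifted to improve balance.

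**The concern.** The protocol gives two reference dates for one severity measure, and two answers on whether it may enter a model. A GINA class taken from the regimen at LMP precedes every study outcome, so the late-measurement argument does not fit it as it fits Asthma Control Test scores or exacerbations during pregnancy. An analyst following Section 9.7.2 would leave the class out; one following Section 9.3.3 would test it as a confounder.

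This matters because the comparator does not by itself equalise severity. Exposed women are severe by indication, while Cohort 2 has no severity quota, matching or trigger for shifting recruitment. Section 9.1 notes that asthma itself is associated with a wide range of adverse pregnancy outcomes. If risk also rises with severity, a raised RR could reflect disease rather than drug.

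**Working it through.** **1. The passages side by side**

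| Question | 9.3.3 | 9.4 | 9.7.2 | 9.7.3 |
|---|---|---|---|---|
| Reference date of the severity class | Enrolment | First day of LMP | After enrolment | Not stated |
| May it be an adjustment factor? | To be considered | Not stated | Typically not | Listed confounders are screened by a 10% change in estimate |
| Severity-stratified analysis | Not stated | Not stated | Possible, if distribution allows | Stated as planned |

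**2. The plan's own figure.** Table 5 (180 exposed, 270 unexposed, 3% birth defects) gives a probability of 0.19 that the observed RR exceeds 1.5 when the true RR is 1. Exact enumeration of two independent binomials gives 0.187. Across the table, 46 of 48 cells agree within 0.02. The other two (3%, threshold 1.2, true RR 1 and 1.2) differ by 0.025 and 0.024, and match once ties at exactly 1.2 are counted.

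**3. Can an adjusted model run?** Section 9.7.1 requires 30 events for logistic regression and 20 for Cox regression.

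- Birth defects, Cohorts 1 and 2: 180 × 0.03 × RR + 270 × 0.03 = 5.4 × RR + 8.1. This gives 13.5 (RR 1), 16.2 (RR 1.5) and 18.9 (RR 2). The probability of 30 or more events is below 0.01% at RR 1 and 0.9% at RR 2. Thirty expected events would need an RR of (30 − 8.1)/5.4 = 4.1.
- If the overall analysis sample includes Cohort 3 (assumed 270 women at 3%, so 8.1 more events): 21.6 to 27.0 expected events, with a 5% to 30% probability of reaching 30.
- SGA, no effect: 450 × 0.10 = 45 events against 30.
- Preterm delivery, no effect: 450 × 0.07 = 31.5 events against 20.

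The SGA and preterm counts are before multiples are excluded. So the default in 9.7.2 has practical force for SGA and preterm delivery, and almost none for the primary endpoint.

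**4. How large could the confounding be?** Let R be the risk ratio for severe against milder asthma and s the severe share of Cohort 2. Assume no drug effect and that all of Cohort 1 is severe. Then expected crude RR = R / (1 + s(R − 1)); for example, R = 1.5 and s = 0.5 give 1.5/1.25 = 1.20. The protocol gives neither R nor s, so both are assumed. The bracketed figure is the probability that the observed birth-defect RR exceeds 1.5, with Cohort 2 prevalence held at 3%; without confounding it is 0.19.

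| s | R = 1.2 | R = 1.5 | R = 2.0 |
|---|---|---|---|
| 10% | 1.18 (0.27) | 1.43 (0.41) | 1.82 (0.62) |
| 30% | 1.13 (0.25) | 1.30 (0.34) | 1.54 (0.47) |
| 50% | 1.09 (0.23) | 1.20 (0.29) | 1.33 (0.36) |
| 70% | 1.05 (0.21) | 1.11 (0.24) | 1.18 (0.27) |

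**The case against.** A reader might infer that the sentence in 9.7.2 is what leaves the primary comparison confounded. The protocol does not support that. The primary estimate is an unadjusted RR by design, and the 30-event rule would almost certainly block an adjusted one even if 9.7.2 were deleted. For the same reason, forcing severity into a propensity score for every comparison would collide with that rule.

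Nor is 9.7.2 a ban. It says typically, and 9.3.3 keeps severity on the covariate list. The protocol also plans balance tables, subgroup and stratified analyses (9.7.3), awareness work aimed at providers of women with more severe asthma (9.2.1) and shifts in recruitment emphasis (9.9). Cohort 2 is not simply a full-spectrum group, since 9.5 stresses severe patients; the 10% row may therefore be pessimistic.

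The mediator argument partly stands. Exposure counts from 8 weeks before LMP (9.3.1), and maintenance users may have started earlier, so the LMP regimen can itself be on-treatment. Part of the date conflict may also be between when the regimen is reported, which is after enrolment, and the date it refers to. But a regimen reported later still describes LMP, and a mediator concern about measures taken during pregnancy does not extend in full to background therapy at LMP.

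Finally, the SAP may settle the details. The default against adjustment and the reason for it, however, are set in the protocol, where they conflict with 9.3.3 and 9.4.

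**Conclusion.** The point holds as an internal contradiction with a plausible consequence. Sections 9.3.3, 9.4 and 9.7.2 disagree on when severity is dated and whether it may be adjusted for; 9.7.2 and 9.7.3 disagree on whether severity-stratified analysis is firm. Following the 9.7.2 default would leave severity out of Cohort 1 versus Cohort 2 models that are expected to run, notably SGA and preterm delivery.

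Residual confounding by severity is plausible, but its size is unknown. The ranges above rest on an assumed severity risk ratio, an assumed severe share of Cohort 2, an entirely severe Cohort 1 and no drug effect. They show that the crude RR could be inflated slightly or substantially, depending mostly on how far Cohort 2 is enriched for severe asthma. Every scenario computed biases upwards, so none of them shows that a real effect would be masked.

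**What to change.** 1. Reconcile 9.3.3, 9.4 and 9.7.2 on one severity class, dated to LMP and based on background therapy with benralizumab itself ignored. Counting benralizumab would tend to place every exposed woman in the top class and remove overlap.
2. Limit the mediator exclusion in 9.7.2 to measures taken during pregnancy (Asthma Control Test, exacerbations). Allow the LMP class as an adjustment factor in Cohort 1 versus Cohort 2 models that meet the 20- or 30-event minimum, for example preterm delivery and SGA. Show results with and without it, because the LMP regimen may partly reflect earlier benralizumab use.
3. For the primary endpoint, commit to an unadjusted RR with exact 95% and 80% CIs restricted to Cohort 2 women in the same background-therapy classes as Cohort 1, reported beside the main estimate. This needs no regression model, and it turns the option in 9.7.2 into the commitment that 9.7.3 already implies.

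Exacerbation history before LMP should not be made part of this: the protocol lists exacerbation events during pregnancy and states no earlier look-back.

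The change is to wording and to the analysis of data already planned for collection. The cost is precision. If 10%, 30% or 50% of the 270 Cohort 2 women with outcomes share the exposed women's classes, the restricted comparator has 27, 81 or 135 women. At 3% that is 0.8, 2.4 or 4.1 expected defects, somewhat more if severity raises risk. The intervals will be wide, and the restricted estimate will be informative only if recruitment does enrich Cohort 2 for severe asthma.

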9.7.3 General considerations for data analyses

The general approach to controlling for confounding is to evaluate each relevant confounder (from a pre-specified list for each outcome) to determine if inclusion of the confounder in a model containing exposure to benralizumab changes the estimate of the effect of exposure by 10% or more. The confounders will be assessed univariately and those confounders that are identified as meeting criteria described above are incorporated into multivariate analyses as described in the statistical analysis Section 9.7.1, if sample size permits. Further details will be contained in the SAP. Control for confounding by indication is addressed by comparison to the treated disease group. However, as described in exploratory analyses in Section 9.7.2, attention to measures of disease symptom control and underlying severity will also be addressed by subgroup and stratified analysis.

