Elective Termination: The proportion of pregnancies ending in elective termination will be compared between the benralizumab exposed group enrolled prior to 20.0 weeks' gestation, and the diseased and non-diseased cohorts enrolled prior to 20.0 weeks' gestation.

Small for Age Postnatal Growth: After exclusion of twins or higher order multiples, the proportion of pregnancies ending in a live born infant \leq 10th centile of postnatal weight, length and/or head circumference will be compared between the benralizumab group exposed anytime in pregnancy and the treated diseased and non-diseased cohorts.

Statistical methods:

Descriptive tables will be prepared for characteristics of each of the cohorts in each interim and final report displaying n, means, standard deviations, minimums and maximums or proportions and percentages.

For the primary endpoint of major structural defects, and for the secondary endpoints of small for gestational age infants, postnatal growth and elective termination, un-adjusted relative risk estimates will be presented together with exact two-sided 95% and 80% confidence intervals.

For the secondary endpoints of preterm delivery, spontaneous abortion, and stillbirth, survival methods will be used (Kaplan Meier) to estimate crude rates and confidence intervals accounting for gestational timing of enrollment in the study.

Adjusted analyses producing relative risks and 95% and 80% confidence intervals or hazard ratios and 95% and 80% confidence intervals, where numbers permit, will be conducted. A minimum of 30 events in the overall analysis sample is required for adjusted analysis for those outcomes assessed with logistic regression. A minimum of 20 events in the overall analysis sample is required for adjusted analysis for those outcomes assessed with Cox Proportional Hazards.

Confounders will be considered for each adjusted analysis separately, using the method of change in estimate of the effect of exposure to benralizumab by 10% or more. If one confounder is identified, direct adjustment will be performed. However, given the expected low frequency of events in a study of this size, if two or more confounders are identified in any given analysis, a propensity score approach for adjustment will be considered. Appropriateness of models will be assessed graphically and by standard statistical methods.

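### Screening confounders one at a time against a 10% change can leave several small same-direction confounders out, so the adjusted SGA and preterm ratios keep part of their joint bias

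*Protocol*

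**What the plan says.** Section 9.7.3 takes candidates "from a pre-specified list for each outcome", adds each one to a model containing benralizumab exposure, and asks whether it "changes the estimate of the effect of exposure by 10% or more". It then says: "The confounders will be assessed univariately and those confounders that are identified as meeting criteria described above are incorporated into multivariate analyses".

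Section 9.7.1 applies the same rule to each adjusted analysis separately, "using the method of change in estimate of the effect of exposure to benralizumab by 10% or more". What follows depends on how many candidates pass:

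- One: "If one confounder is identified, direct adjustment will be performed".
- Two or more: "if two or more confounders are identified in any given analysis, a propensity score approach for adjustment will be considered".

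Adjustment is also subject to event floors. For logistic outcomes: "A minimum of 30 events in the overall analysis sample is required for adjusted analysis for those outcomes assessed with logistic regression". For time-to-event outcomes: "A minimum of 20 events in the overall analysis sample is required for adjusted analysis for those outcomes assessed with Cox Proportional Hazards".

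The protocol states no forced covariate set, no joint or backward step, and no comparison of the crude ratio with one adjusted for the whole list. Further detail is left to the SAP, but the selection rule itself is fixed here.

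**The concern.** Confounding from several variables acts jointly, whereas the rule judges each variable alone. A covariate that shifts the ratio by 6% fails the test, and so do five others like it, although together they may shift it by 40%. If none passes, the adjusted ratio is simply the crude ratio.

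The propensity score does not recover what was lost, because the same screen decides when it is considered. Section 9.7.1 justifies it by the low expected number of events. That is a reason to use it on the full list, since the size of a propensity model is limited by the number of exposed women and not by outcome events.

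Section 9.3.3 lists many candidates, including age, parity, education, socioeconomic status, body mass index, previous preterm delivery, comorbidity, smoking and alcohol. Interpretation rests on point estimates and intervals without testing (section 9.5). Residual bias could therefore be read as a drug signal or, in the other direction, hide one.

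**Working it through.** **Inputs from the protocol.** Section 9.5 and Table 5: 180 exposed and 270 treated-asthma women with complete outcome; comparison-group prevalence 3% (major defects), 7% (preterm birth), 10% (SGA). Sections 9.7.1 and 9.7.3: threshold 10%; floors of 30 events (logistic) and 20 (Cox).

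**Inputs assumed.** The number, prevalence, strength and direction of confounders. The protocol gives none of these.

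**1. Table 5 reproduced.** Exact enumeration of two independent binomials gives P(observed RR > 1.5) at a true RR of 1 as 0.187, 0.103 and 0.067. Table 5 has 0.19, 0.10 and 0.07.

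**2. Where adjustment will happen.** Expected events in the two asthma cohorts, at true RR 1 and RR 2:

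| Outcome | RR 1 | RR 2 | Floor |
|---|---|---|---|
| Major defects | 0.03 × 450 = 13.5 | 8.1 + 10.8 = 18.9 | 30 |
| Preterm birth | 0.07 × 450 = 31.5 | 18.9 + 25.2 = 44.1 | 20 |
| SGA | 0.10 × 450 = 45 | 27 + 36 = 63 | 30 |

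For major defects P(≥30 events) is at most 0.01. If the floor counts the third cohort as well, and 3% is assumed there, expected events are 21.6 to 27.0 and P(≥30) is 0.05 to 0.30. For preterm birth P(≥20) is at least 0.99, and for SGA P(≥30) is at least 0.99.

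**3. Joint bias by hand.** For one binary confounder the bias factor is (1 + p1(RR − 1)) / (1 + p0(RR − 1)). With 42% vs 30% and a risk ratio of 1.6 it is 1.252 / 1.180 = 1.061. Adjusting for that covariate alone moves the ratio by 1 − 1/1.061 = 5.7%, below the threshold. Six independent ones give 1.061^6 = 1.43.

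**4. The rule applied at the study's size.** Simulation with 180/270, SGA 10% in the unexposed, true odds ratio 1, logistic models and six such confounders (odds ratio 1.6 each):

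| Analysis | Mean odds ratio | Range over repeat runs |
|---|---|---|
| Crude | 1.43 | 1.38 to 1.43 |
| After the 10% screen | 1.27 | 1.24 to 1.29 |
| Propensity score on all six | 1.01 | 0.98 to 1.02 |

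The SD of the log odds ratio was 0.338 after the screen and 0.331 with the full score. The screen left ln 1.27 / ln 1.43 = 0.239 / 0.358 = 67% of the log bias. It selected nothing in 40% to 44% of studies.

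**5. Other settings.**

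- Five confounders, 45% vs 30%, odds ratio 1.7: crude 1.51, after the screen 1.23. Remaining: ln 1.23 / ln 1.51 = 50%.
- Three of the same kind: 1.25 and 1.09. Remaining: ln 1.09 / ln 1.25 = 39%.
- Ten weak ones, 38% vs 30%, odds ratio 1.5: 1.38, 1.32 after the screen, 0.99 with the full score.
- Three harmful and three protective: 1.02, 1.02 and 1.01.
- Four against two: 1.13, 1.08 and 1.00.

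**6. What a residual of this size does.** At 10% risk an odds ratio of 1.27 is a risk ratio of 1.27 / (0.9 + 0.127) = 1.24. The binomial calculation of step 1 with that bias raises P(observed RR > 1.5) for SGA from 0.07 to about 0.21.

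**The case against.** Change-in-estimate screening is a recognised, if dated, method, and several objections to this point have force.

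- **Invented inputs.** No section says that the asthma cohorts will differ on many factors, all in one direction. Section 9.9 names disease severity, other exposures and treatment patterns, and section 9.7.2 keeps severity out of routine adjustment. This stands: the size is an assumption, and it shrinks or vanishes with mixed directions.
- **Primary endpoint.** Major defects will probably be reported unadjusted whatever the screening rule. This stands and limits the scope.
- **Precision.** In step 4 every covariate was a true confounder. With two true confounders and fifteen covariates related to exposure only (50% vs 30%), the SD of the log odds ratio was 0.447 for the full score, 0.408 for the screen and 0.330 crude; root mean squared error was 0.447, 0.419 and 0.352. The full score does worse there, so the list must be chosen with care.
- **Deferral to the SAP.** Section 9.3.3 promises more detail on identifying and controlling confounders, and the content of the propensity score is not stated. This stands only in part. The one-at-a-time rule is already fixed, and a full-list score used only after two confounders have passed helps little (1.25 against 1.29 in one run).
- **Existing safeguards.** Crude ratios with 95% and 80% intervals and descriptive cohort tables are planned, and section 9.9 admits that not every covariate may be controlled. These disclose the problem without removing it.

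**Conclusion.** The concern holds as a weakness of a stated rule, with a size that depends on assumptions. If several confounders act in the same direction and each falls short of 10%, the adjusted ratio keeps part of their joint bias: about two thirds on the log scale for six moderate confounders, about half or somewhat less for three to five stronger ones, and almost none when directions balance. Adjusting for the full list of true confounders removed the bias at the same SD.

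A reader might infer more, and the documents do not support it:

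- **That all such confounders are always dropped, or that most of the bias always stays.** At this sample size chance carries some over the threshold.
- **That the reported ratio would be biased to about 1.5.** A figure of that order is the crude bias under five strong independent confounders; the ratios after screening in step 5 were 1.09 to 1.32 where all confounders acted in one direction.
- **That the primary result is distorted by the screen.** With 13.5 to 18.9 expected events it should not reach adjustment.

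The practical consequence falls on SGA and preterm birth. The change is a cheap improvement and not a correction of an invalid analysis.

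**What to change.** For Cohort 1 vs Cohort 2, replace the 10% screen in sections 9.7.1 and 9.7.3 with adjustment for the whole pre-specified, outcome-specific list through one propensity score, whatever the change in estimate. Apply it only to outcomes that meet the existing floors of 30 and 20 events.

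Limit the list to pre-exposure variables that are known or suspected risk factors for the outcome, and leave out variables related to exposure only. Some entries in section 9.3.3, such as pregnancy-induced hypertension and gestational diabetes, arise after early exposure and would not qualify. Report standardized differences before and after adjustment, and keep the planned crude ratio alongside.

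The cost is protocol and SAP wording plus the propensity model, on covariates already collected. Balance and extreme scores must be checked, and some precision is lost if many exposure-only variables enter the list.
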